**Please answer the following questions by ticking the correct box:**

1. Have you had any health problems since your last visit to clinic?

Yes  No

2. Have you had any local skin reactions since your last visit to clinic?

Yes  No

3. Have you taken any new medications since your last visit to clinic?

Yes  No

*In case of medical emergency call 911 immediately.*

**Remember the next study visit date is Day 28 i.e. 14 days from Visit 4 (Day 14): \_\_\_\_\_**

***Subject's Initials:*** \_\_\_ - \_\_\_ - \_\_\_

***Date:*** \_\_\_\_ - \_\_\_\_ - \_\_\_\_

***Initials of Site Staff verifying the completeness of the Subject Diary:*** \_\_\_ - \_\_\_ - \_\_\_

***Date of Verification:*** \_\_\_\_ - \_\_\_\_ - \_\_\_\_

## 12.4 Appendix D. Patient Self-Assessment

PROTOCOL NO: MAP-8184	SUBJECT NUMBER :							Subject Initials:	
---------------------------------	-------------------------	----------------------	----------------------	----------------------	----------------------	----------------------	----------------------	--------------------------	----------------------

Visit Number	Visit 2 [Baseline]	Visit 3 [Interim]	Visit 4 [Interim]	Visit 5 [EOS/ET]
Visit Day	Day 1	Day 7	Day 14	Day 28
Check one				

**VISIT DATE :**

D      D      M      M      M      Y      Y      Y      Y

This self-assessment is aimed to see how bad are the itching and stinging/burning sensations that you may experience during the last 24 hours. Please rate these feelings by marking one most suitable option from each table below.

### ITCHING

(Intense, distracting irritation or tickling sensation in the last 24 hours)

Score	Grade	Definition	Check one
0	None	No Itching	
1	Mild	Barely perceptible, slightly present itch	
2	Moderate	Distinct presence of itch	
3	Severe	Marked, intense, yet tolerable itch	
4	Very Severe	Unbearable, intense itch	

### STINGING/BURNING

(Sensation of the skin is painfully hot or noticeable tingling sensation in the last 24 hours)

Score	Grade	Definition	Check one
0	None	Absent	
1	Mild	Slight, barely present	
2	Moderate	Distinct presence	
3	Severe	Marked, intense	

Subject Initials: \_\_\_\_\_

Date: \_\_\_\_\_

1. INTRODUCTION

This document describes the statistical methods and data presentations to be used in the summary and analysis of data from Protocol MAP-8184. Background information is provided for the overall study design and objectives. The reader is referred to the study protocol and electronic case report forms (eCRFs) for details of study conduct and data collection.

1.1. Study Overview

Clinical protocol MAP-8184 is a multicenter, randomized (1:1), double blind, two-arm parallel group study to compare the treatment success of the test product, Permethrin Cream, 5% (Mayne Pharma, Inc.), and the Reference product, Elimite™ (marketed by Prestium Pharma, Inc.) on scabies infestations.

This study assesses the comparative efficacy of Permethrin Cream, 5% (Mayne Pharma, Inc.) and Elimite™ in patients with scabies infestation at the end of the treatment period (28±4 days).

The study also assesses comparative safety of Permethrin Cream, 5% (Mayne Pharma, Inc.) and Elimite™ and tolerability of Permethrin Cream, 5%.

This study is comprised of two phases: screening and treatment. The screening period will be up to 5 days in duration and treatment will be 28±4 days in duration. Please refer Table 1.2 below for a more detailed presentation of the study visits and assessments. After signing informed consent during screening (Visit 1), subjects, at least 12 years of age, male or female, of any race, will be evaluated to determine if they meet inclusion/exclusion criteria. Any subject under the age of 18 must sign the Assent Form and have the signature by a parent or legal guardian on informed consent form prior to enrollment in this study. Eligible patients will be enrolled and randomized in a 1:1 ratio for Test and Reference, and will be stratified by site. Following the receipt of informed consent, the subject's medical history will be recorded along with concomitant medications and prohibited treatments will be assessed as they should be discontinued. A physical examination will be performed for all subjects and a urine pregnancy test will be performed for women of childbearing potential. The subject's scabies infestation will be evaluated for papules and burrows during the visual examination. Presence of acarids, feces, or ova will be assessed via microscopic exam of skin lesion scraping. Subjects who meet all inclusion/exclusion criteria will return to the office for visit 2 within 5 days.

At Visit 2 (Baseline, Day 1), the subject's concomitant medications will be updated and any changes to medical history will be recorded. If subjects meet the randomization criteria, they will be assigned to one of the two treatment arms (Test or Reference) and the respective investigational product will be dispensed to subjects along with detailed instructions of drug application. The subjects also will be instructed on completion of subject diaries. Visits 1 and 2 can be combined, if subject's eligibility can be confirmed at the Screening visit and conducted on the same day,

which then is Day 1. All regular bedmates of the subject and individuals with prolonged physical contact with the subject will undergo an assessment by the Investigator and receive one 60 g tube of the standard of care generic Permethrin Cream, 5% at the Baseline visit, sufficient for two applications to prevent cross-infestation within the household.

Subject will return at visit 3 (Day 7±1) with the used investigational product tube and subject diaries. Compliance with investigational product applications will be assessed. Safety and tolerability assessments will be conducted.

At visit 4 (Day 14±2), subjects will return for efficacy, safety and tolerability assessments. If signs of active scabies infection are present at this visit, the subject will be treated with a second application of their assigned investigational product.

Final efficacy, safety and tolerability assessments will occur at visit 5 (Day 28±4). If the subject was retreated, the used tube of the investigational product will be returned at this visit. The duration of each subject's participation in the study will be a maximum of 37 days.

Subjects will be encouraged to report any complications or adverse effects during their participation. Investigator may evaluate the subject at an unscheduled visit, if subject's condition will be considered as worsening. If the Investigator assesses the subject's condition at any time and determines that the subject's condition has worsened to the degree that it is unsafe for the subject to continue in the study, the subject may be discontinued from the study as treatment failure. Visit 5 Early Termination procedures will be performed, and a standard of care treatment may be advised at the Investigator's discretion.

1.2. Time and Events Schedule

TABLE 1.2 Study Procedures and Assessments.

Visit Number	Visit 1 Screening	Visit 2 Baseline ¹	Visit 3 Interim	Visit 4 Interim	Visit 5 EOS/ET ²
Visit Day	Day -5 to 1	Day 1	Day 7 (±1)	Day 14 (±2)	Day 28 (±4)
Informed Consent	X				
Eligibility Criteria	X				
Subject Demographics	X				
Medical History	X				
Physical Exam	X ³				
Randomization		X ⁴			
Vital Signs	X	X			X
Urine Pregnancy Test ⁵	X				X
Visual Examination of Lesions	X	X	X	X	X
Microscopic Examination of Skin Scraping ⁶	X				
Patient Self-Assessment		X	X	X	X
Investigational Product Dispensation		X		X ⁷	
Treatment with Investigational Product		X		X ⁷	
Investigational Product Accountability			X		X ⁸
Subject Diary Compliance Review			X		X ⁸
Concomitant and Prohibited Medication Review	X	X	X	X	X
Adverse Events Assessment		X ⁸	X	X	X

1. Visit 2 (Baseline) may be completed on the same day as visit 1 (Screening). If Screening and Baseline are completed on the same day, assessments performed on both screening and baseline need only be performed once.
2. End of Study/Early Termination
3. Physical examinations are to be performed if Inclusion/Exclusion Criteria are satisfied at Screening
4. Prior to Randomization, the Investigator must confirm the subject still meets all Inclusion/Exclusion Criteria.
5. For females of child-bearing potential
6. Any new lesions identified at Visits 3, 4, or 5 will be confirmed by microscopic evaluation of skin scraping
7. Applicable for subjects requiring second application of the investigational product
8. AE reporting period for this study begins from the time of application of the investigational product and ends at the final protocol required visit

1.3. Glossary of Terms

AE	Adverse Event
CRA	Clinical Research Associate
CRF	Case Report Form
CTMF	Clinical Trial Master File
CTP	Clinical Trial Protocol
eCRF	Electronic Case Report Form
GCP	Good Clinical Practice
IB	Investigator's Brochure
ICH	International Conference On Harmonization
IEC	Independent Ethics Committee
IGE	Investigator's Global Evaluation
IP	Investigation Product
IRB	Institutional Review Board
ISF	Investigator Site File
LOCF	Last Observation Carried Forward
mITT	Modified Intent-To-Treat
PP	Per-Protocol
PD	Protocol Deviation
PDRR	Protocol Deviation Review Request
SAE	Serious Adverse Event
SOP	Standard Operating Procedures
SUSAR	Suspected Unexpected Serious Adverse Reactions

2. OBJECTIVES

The primary objective of this study is:

- To demonstrate bioequivalence between Permethrin Cream, 5% (Mayne Pharma, Inc.) and Elimite™ in patients with active scabies.

The secondary objective of this study is:

- To demonstrate comparative safety of Permethrin Cream, 5% (Mayne Pharma, Inc.) vs Elimite™ and tolerability of 5% Permethrin cream.

3. GENERAL STATISTICAL CONSIDERATIONS

3.1. Sample Size Estimation

Under the assumption that the Reference product has a cure rate of at least 88%, sample size evaluations were conducted, via computer simulation, to determine the probability (power) of the calculated 90% continuity-corrected confidence interval on the Test-to-Reference difference in cure proportions to be contained in the bioequivalence interval [-0.20, +0.20]. When the Test product was assumed to have the same 88% cure rate, the required number of PP subjects in each treatment group was determined to be 56 (112 total) for a power ≥ 0.80 . Assuming 20% of drop-out rate, 70 subjects in each treatment group (140 total) would be needed.

If it is assumed that the Test product cure rate might deviate from that of the Reference by as much as 2% (e.g. 86% instead of 88%) and if a higher power, ≥ 0.95 , was desired, then 91 PP subjects in each treatment group (182 total) would be needed. Assuming 20% drop-out rate, 114 subjects in each treatment group (228 total) would need to be enrolled.

3.2. Randomization

The actual treatment given to individual subjects is determined by a computerized block randomization scheme prepared by an independent third party. The independent third party will prepare the randomization list and hold it throughout the conduct of the study. The content of the randomization list will not be available to either clinical sites or sponsor up until the database is locked. Subjects are randomized on a 1:1 basis (test drug: active comparator) in blocks of two and stratified by clinical site. The subject randomization number corresponds to either one of the active drugs treatment allocation.

Clinical sites will contact the independent third party responsible for the randomization scheme at the time subject has met all inclusion criteria and is ready for enrollment. Blocks of two (2) tubes will be supplied to the sites. Site's dispensing pharmacist will randomly select a tube with an

investigational product from the block for the study subject. Next enrolled subject will receive the remaining investigational product from the same block until the block is entirely used. Subject eligibility is established before treatment randomization at Visit 2 (Screening and Visit 2 Randomization can be combined into one visit). Subjects are randomized strictly sequentially, as subjects are eligible at the clinical sites.

After signing the Informed Consent, each subject will be assigned a unique subject number. Subjects are identified using subject initials, subject number, and date of birth. The subject numbers will be generated by the EDC and assigned sequentially in the order in which subjects are consented at each center.

If a subject discontinues from the study, the subject number and randomization number are not to be reused, and the subject is not allowed to re-enter the study.

Based on the clinical judgement and requirements described in the protocol, the Investigator may provide a retreatment to the study subject. Only one retreatment is allowed per subject. The retreatment assignment must belong to the same treatment arm. In order to dispense the correct treatment, the following process is to be followed:

1. Study pharmacist will contact the Drug Depot, specifying subject's identifying information.
2. Drug Depot will specify which kit number shall be dispensed for retreatment.

The randomization scheme for treatment allocation will be used for statistical and reporting purposes. A sealed copy of the randomization assignment will be retained at each clinical site and will be available to FDA or other regulatory agency investigators at the time of site inspection to allow for verification of the treatment identity of each subject.

3.3. Blinding and Procedures for Unblinding the Study

This is a double-blind study in which the study subjects, the Investigator, the Study Coordinator, clinical staff, Sponsor (with the exception of the independent third party who generated the randomization code), and any personnel involved in the monitoring, evaluation, and analysis of study data will not be aware of treatment assignment for any subject until after the database for the study has been finalized. Members of the Data Monitoring Committee may, on occasion, use the treatment assignment codes provided by the unblinded statistician at the independent third party to determine the treatment assignment of a subject reviewed by the committee.

The packaging of the test and the reference products will be similar in appearance to make difference in treatment less obvious to the subjects. To maintain adequate blinding of Investigators and subject evaluators, it is recommended that the investigational product dispensation and accountability be performed by the study pharmacist, or designated study personnel who will not

be involved in any other activities of this study. Neither the Investigator nor the patient should be able to identify the received treatment. The dispensed investigational product will NOT be opened by the subject at the study center except in front of the study pharmacist, or designated study personnel. The randomization scheme will not be available to the physician, the study pharmacist or designated study personnel for investigational product dispensation and accountability and nursing staff or study coordinators involved in the collection, monitoring, revision, or evaluation of adverse events or to clinical staff who could have an impact on the outcome of the study.

A sealed copy of the randomization code will be supplied with each block of the investigational product and will be retained at each clinical site. Randomization codes must be available to the FDA or other regulatory agency investigators at the time of site inspection to allow for verification of the treatment identity of each subject.

From Day 1 through the end of the study, the randomization code must not be broken except in emergency situations for which the identification of the study treatment of a subject is required by the Qualified Investigator for subject safety and medical care. In the event of a medical emergency requiring identification of the study drug administered to an individual subject, Investigator will make every attempt to contact the Biorasi Project Manager by telephone, explaining the need for unblinding, before or no later than 24 hours of breaking the blinding. The Investigator must document the time, date, and reason for the unblinding and the names of the personnel involved on the CRF, in the site file, and in the medical notes. The Investigator must notify the Sponsor in writing as soon as possible following the unblinding event explaining the necessity of unblinding of the investigational product(s). Every effort should be made to avoid unblinding extra study personnel.

3.4. Handling of Data

3.4.1. Examination of Subject Subsets

The primary and secondary efficacy endpoints will be summarized separately using descriptive statistics by treatment group and study day, where appropriate. No formal statistical testing will be utilized.

3.4.2. Missing Data

Every effort will be made to obtain required data at each scheduled evaluation from all subjects who have been randomized. In situations where it is not possible to obtain all safety data, imputation of missing data will not be conducted. A Last-Observation-Carried-Forward imputation method for missing efficacy data will be used for the mITT population.

3.4.3. Definitions and Terminology

Treatment Day 1 (Baseline)

Treatment Day 1 is the day that study treatment is first initiated.

Study Day

Study Day is defined relative to study treatment initiation (Study Day 1). Thus, the study day of an event is calculated as:

$$\text{Study Day} = \text{event date} - \text{date of Study Day 1} + 1.$$

Days on Study

Days on Study is the number of days from Study Day 1 to the date of study completion or early termination as recorded on the study termination eCRF.

End of Treatment

For efficacy assessments, end of treatment is defined as the last non-missing assessment taken prior to discontinuation of study treatment.

Concomitant Medications

Concomitant medications are those medications taken on or after the initiation of study treatment. This definition includes prescription and all over-the-counter (OTC) medications and all dietary supplements.

Previous Medications

Previous medications are those medications taken within the 30 days and stopped prior to the initiation of study therapy.

Treatment-Emergent Adverse Event

A treatment-emergent adverse event is defined as any adverse event occurring on or after the initiation of study treatment. For the purpose of defining treatment-emergent adverse events, it is assumed that an adverse event which was reported to have started on Treatment Day 1 without an associated onset time may have occurred after the initiation of study treatment. Hence, adverse events occurring on Treatment Day 1 are assumed to be treatment-emergent.

3.5. Planned Analyses

A final analysis is planned after the last subject completes or discontinues the study, and the resulting clinical database has been cleaned, quality checked, and locked.

4. ANALYSIS POPULATIONS

The populations defined for analysis will include the modified intent-to-treat (mITT), per-protocol (PP), and the safety population.

Safety population: The safety population is any randomized individual who: (a) was enrolled into the study, and (b) received at least one application of study treatment. Subjects will be analyzed according to the treatment received. This population will be used for safety assessment.

Modified Intent-to-Treat (mITT): A modified intent-to-treat subject is any randomized individual who: (a) was enrolled into the study, (b) met inclusion/exclusion criteria, (c) received at least one application of study treatment, and (d) had at least one post-baseline visit. Subjects will be analyzed according to the randomized treatment. This population will be used for secondary and primary efficacy analysis as supportive analysis.

Per Protocol (PP): A per-protocol subject is any randomized individual who: (a) enrolled into the study and met inclusion/exclusion criteria, (b) received the assigned study treatment, (c) had not taken any concomitant medications prohibited by the protocol or experienced any major deviations that interfered with or may have interfered with the therapeutic administration of the treatment or the precise evaluation of treatment efficacy, and (d) completed the primary endpoint evaluation within the designated visit window (± 4 days).

Subjects whose condition worsens and require alternate or supplemental therapy for the treatment of scabies during the study will be discontinued, included in both the mITT and PP population analyses as treatment failures. Subjects who discontinue early for reasons other than treatment failure will be excluded from the PP population, but included in the mITT population, using Last Observation Carried Forward (LOCF).

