### **4.3 Withdrawal and Early Discontinuation**

In accordance with the Declaration of Helsinki and other applicable regulations, a subject has the right to withdraw from the study at any time and for any reason without prejudice to his or her future medical care. The Investigator, Sponsor, or Medical Monitor may also withdraw the subject at any time if it is medically necessary or in the interest of subject safety.

A subject will be discontinued from this study if any of the following criteria are met:

- Withdrawal of consent by the subject is received
- In the opinion of the Investigator, it is not in the subject's best interests to continue in the study.
- Occurrence of an AE/SAE, which, in the opinion of the Investigator, warrants discontinuation of the subject from the study.
- Pregnancy
- Significant non-compliance with study procedures that would interfere with the study results or increase the subject's risks in the study. This includes known cases of non-compliance of household members with the standard of care treatment.
- If subject is deemed to be a treatment failure, which is defined as any subject whose condition worsens and who requires alternate or supplemental therapy for the treatment of scabies during the study.

Subjects discontinuing, or withdrawing from, the study sooner than their Day 28 visit will undergo the End of Study assessments (as detailed in Section 6.3.5). In addition, if the subject is discontinuing the study and has not returned the dispensed Investigational Product, then the site will remind the subject to return the dispensed investigational product during the End of study visit. In such cases, the Investigational Product dispensed to the subject will be collected and Investigational Product accountability will be performed as per Section 5.10 during the End of Study visit (see Schedule of Activities in Appendix B).

After the End of Study visit, the subject may resume dosing with any medication prescribed by the subject's physician, including Prohibited Medications listed in section 5.11.

If a subject does not return for a scheduled visit, every effort will be made to contact the subject and

document the End of Study visit assessments. The Investigator must document the primary reason for discontinuation of a study subject on the appropriate electronic Case Report Form (CRF).

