##### **5.6.1 Assignment of Retreatment**

Based on the clinical judgement and requirements described in the protocol, the Investigator may provide

a retreatment to the study subject. Only one retreatment is allowed per subject. The retreatment assignment must belong to the same treatment arm. In order to dispense the correct treatment, the following process is to be followed:

1. Study pharmacist will contact the Drug Depot, specifying subject's identifying information.
2. Drug Depot will specify which kit number shall be dispensed for retreatment.

Please refer to the study *Pharmacy Manual* for details.

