### 5.11 Prior, Concomitant and Prohibited Therapy

Current medications and any medications taken within the 30 days prior to the start of the study will be recorded as prior/concomitant medications (using their generic name, if known) with the corresponding indication. The medications to be recorded include prescription and all over-the-counter (OTC) medications and all dietary supplements. All medications taken on a regular basis, including aspirin and acetaminophen, should be recorded prior to commencing the use of the investigational product. Any medications started during the study (including “as needed” medications) will be recorded in the concomitant medication list as soon as the Investigational Site will become aware of the medication being added.

If the Investigator becomes aware of a subject having taken a prohibited medication, they will report the incident to the Medical Monitor and Biorasi within 24 hours, and the Medical Monitor and/or Sponsor will provide written approval of the subject’s continuation or discontinuation in the study.

Prohibited medications include:

- 1 Topical or oral scabicial/antiparasitic treatment including: permethrin, benzyl alcohol, benzyl benzoate, lindane, crotamiton, malathion, ivermectin, precipitated sulfur, albendazole, keratolytic cream, tea tree oil, or oil of the leaves of Lippia multiflora Moldenke within 28 days of visit 2.
- 2 Systemic corticosteroids (including inhaled steroids) taken within 14 days of visit 2.
- 3 Topical corticosteroids including hydrocortisone taken within 24 hours of visit 2.
- 4 Topical antipruritics, including antihistamines within 24 hours of any study visits.
- 5 Oral antihistamine including diphenhydramine (Benadryl) taken within 24 hours of any study visits.
- 6 Topical antibiotics including mupirocin taken within 24 hours of any study visits.

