### 8.1 Subject Population/Data Sets to Be Evaluated

The subject populations are defined as follows:

1. **Safety Population:** The safety population is any randomized individual who (a) was enrolled into the study, and (b) received at least one dose of study treatment.
2. **Modified Intent-to-Treat (mITT) Population:** A modified intent-to-treat subject is any randomized individual who (a) met inclusion/exclusion criteria, (b) was enrolled into the study, (c) received at least one dose of the assigned study treatment, and (c) had at least one post-baseline visit.
3. **Per Protocol (PP) Population:** A per-protocol subject is any randomized individual who (a) met inclusion/exclusion criteria, (b) was enrolled into the study, (c) received the assigned study treatment, (d) had not taken any concomitant medications prohibited by the protocol or experienced any major deviations that interfered with or may have interfered with the therapeutic administration of the treatment or the precise evaluation of treatment efficacy, and (e) completed the primary endpoint evaluation within the designated visit window ( $\pm 4$  days).

Subjects whose condition worsens and require alternate or supplemental therapy for the treatment of scabies during the study will be discontinued, included in both the mITT and PP population analyses as treatment failures. Subjects who discontinue early for reasons other than treatment failure will be excluded from the PP population, but included in the mITT population, using Last Observation Carried Forward (LOCF).

Efficacy analyses will be performed using the per-protocol population as definitive and the mITT population as supportive. Safety analyses will be performed using the Safety population.

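### Subjects whose scabies persists without worsening drop out of the definitive PP set if they leave for lack of effect or use another scabicide, so PP membership depends on outcome

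*SAP*

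**What the plan says.** Protocol 4.3 lists treatment failure among the reasons for discontinuation, "defined as any subject whose condition worsens and who requires alternate or supplemental therapy for the treatment of scabies during the study". Both conditions must hold. Protocol 8.1 and SAP section 4 carry the same joint condition into the analysis sets: "Subjects whose condition worsens and require alternate or supplemental therapy for the treatment of scabies during the study will be discontinued", and these subjects count as failures in both mITT and PP. For everyone else who leaves early, SAP section 4 states: "Subjects who discontinue early for reasons other than treatment failure will be excluded from the PP population". They stay in mITT with the last observation carried forward.

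PP further requires that the subject "had not taken any concomitant medications prohibited by the protocol" and has not "experienced any major deviations that interfered with or may have interfered with the therapeutic administration of the treatment" or the evaluation of efficacy. Protocol 5.11 lists scabicides as prohibited, but the entry ends "oil of the leaves of Lippia multiflora Moldenke within 28 days of visit 2", which reads partly as a washout.

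The PP result is definitive and mITT is supportive (Protocol 8.3.2, SAP 5.2.1).

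**The concern.** Consider a subject whose scabies neither clears nor worsens. If that subject stops for lack of effect, the early-discontinuation rule removes the subject from PP. If the subject uses another scabicide, the prohibited-medication clause applies. Should that clause be read as washout only, the major-deviation clause applies instead. No other section returns the subject to PP as non-cured.

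The protocol leaves room for both routes. Under 4.3, "a subject has the right to withdraw from the study at any time and for any reason". Under 5.6.1, "Only one retreatment is allowed per subject". Section 6.3.5 allows the Investigator to discontinue a subject at any time and advise standard of care, without tying this to worsening. That section also words treatment failure differently from 4.3 (worsening to the point that continuing is unsafe), and the two wordings need to be reconciled. Both rest on worsening, so neither closes the gap.

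The subjects removed are failures. If equal shares of failures go from each arm, the observed difference shrinks and equivalence is easier to declare. If removals fall mainly in the better arm, the bias runs the other way. Whether a non-cure counts would turn on whether worsening was recorded.

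**Working it through.** **Inputs.** Limits ±0.20, a 90% interval with multiplier 1.645, and the continuity correction (Protocol 8.3.2). Reference cure rate 88%; 56 PP subjects per arm, or 91 if enrolment expands (Protocol 8.2, SAP 3.1). The share f of non-cured subjects lost from PP by these routes is an assumption, because the documents give none.

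**Decision rule.** se = √[p_T(1−p_T)/n_T + p_R(1−p_R)/n_R]. L and U are (p_T − p_R) ∓ [1.645·se + (1/n_T + 1/n_R)/2]. Equivalence needs L ≥ −0.20 and U ≤ 0.20.

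**Plan's own figures.** Exact binomial enumeration of this rule gives power 0.817 at 88%/88% with 56 per arm (planned ≥ 0.80) and 0.952 at 86%/88% with 91 per arm (planned ≥ 0.95). Enrolment: 56/0.8 = 70, and 91/0.8 = 113.75, rounded up to 114. The stated sizes reproduce.

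**Shift in PP cure rates.** With share f of non-cures removed, the PP cure rate is p/[p + (1−p)(1−f)]. At f = 0.10, Test is 0.68/(0.68 + 0.32×0.90) = 0.702 and Reference is 0.88/(0.88 + 0.12×0.90) = 0.891. A true difference of −0.20 becomes −0.188.

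**Chance of declaring equivalence at true 68% vs 88%, equal f.** Each non-cured subject is removed with probability f, summed over all outcomes; n is the PP size before these removals.

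| f | 56 per arm | 91 per arm |
|---|---|---|
| 0 | 3.1% | 3.5% |
| 0.05 | 3.8% | 4.4% |
| 0.10 | 4.5% | 5.4% |
| 0.20 | 6.6% | 8.5% |
| 0.30 | 9.8% | 13.4% |

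The 5% level is crossed at f ≈ 0.127 with 56 per arm and f ≈ 0.082 with 91 per arm. At 56 per arm that crossing means an expected 56×0.32×0.127 ≈ 2.3 Test and 56×0.12×0.127 ≈ 0.9 Reference subjects.

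**Unequal f at 56 per arm.** Test 0.2, Reference 0: 10.8%. Test 0.2, Reference 0.4: 3.6%. Test 0, Reference 0.2: 1.6%.

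**Single-subject examples.**

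| Test vs Reference cured | Change from its starting case | L | Equivalent? |
|---|---|---|---|
| 45/56 vs 49/56 | starting case A | −0.0714 − 0.1136 − 0.0179 = −0.2029 | no |
| 45/55 vs 49/56 | A, one Test failure removed | −0.1871 | yes |
| 45/54 vs 49/55 | A, two Test and one Reference removed | −0.1843 | yes |
| 45/55 vs 49/55 | A, one removed per arm | −0.2009 | no |
| 46/56 vs 50/56 | starting case B | −0.1975 | yes |
| 46/56 vs 50/55 | B, one Reference failure removed | −0.2113 | no |

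U is below 0.20 in every row.

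**How often the decision moves at f = 0.10, 56 per arm.** At Test 68%, it moves to equivalence with probability 1.8% and away with 0.4%. At Test 78%, the figures are 6.9% and 2.2%. Test 78% lies inside the limits, so that pair shows instability rather than error.

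**The case against.** The exposed group is probably small. Active scabies at Day 14 leads to a second application of the assigned product (Protocol 5.8.1), and a subject still uncured at Day 28 with no PP exclusion stays as a non-cure. With f assumed, the error rate at 56 per arm stays below 5% for small equal f. The 91-per-arm figures apply only if more Reference product arrives. The direction under unequal f is unknown, and any PP exclusion can flip a result already at the boundary. Early leavers remain in mITT, where carrying the last observation forward would normally keep them as not cured, and the planned listings would identify them. A sensitivity analysis could show the effect without changing the definitive set.

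The points on size and direction stand, and they limit the weight of the concern. The rest does not remove it. mITT, the listings and a sensitivity analysis make the problem visible but leave the PP rule that decides the trial unchanged. The washout reading of 5.11 moves scabicide use from one PP exclusion clause to another. Scoring recurrence as non-cure fits an endpoint that already requires no new lesions.

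**Conclusion.** The concern holds. As written, the definitive set drops certain non-cures because worsening was not recorded. At the current 56 per arm, with equal removal and a true difference at the limit, the false-equivalence rate rises from 3.1% to 4.5% at f = 0.10 and 6.6% at f = 0.20. It exceeds 5% only beyond f of about 0.127. Unequal removal gave between 1.6% and 10.8% in the cases computed. These sizes rest on an f that the documents do not supply. The gap in the definition does not depend on f. The change should be made, with medium confidence in how much it matters. The sample-size calculation is not in question.

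A lesser point, which does not affect the decision: no rule stops a scabicide user who is allowed to continue and is clear at Day 28 from counting as cured in mITT.

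**What to change.** In SAP section 4 and Protocol 8.1, add a rule for analysis classification only; it does not govern who receives other therapy. Score as non-cured, in both PP and mITT, any otherwise eligible dosed subject who either:

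- has a non-study scabicide recorded before the Day 28 assessment with persistent or recurrent scabies as the indication, whether or not worsening was recorded; or
- has lack of effect as the recorded primary reason for discontinuation.

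State that this rule takes precedence over the PP exclusions for prohibited medication, major deviation (for that scabicide use), early discontinuation and visit window. As a drafting clarification, say the same for the existing treatment-failure rule.

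**Cost.** A short paragraph in each document. Indications and the primary reason for discontinuation are already recorded (Protocol 6.2.1.7 and 4.3); the eCRF reason list must include lack of effect. Power at 88%/88% with 56 per arm is the planned 81.7%, instead of the 84.1% (f = 0.10) or 87.0% (f = 0.20) obtained by deleting failures.

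The main risk is miscounting cured subjects who self-treat residual itch. If 2% or 5% of cured subjects per arm were misclassified (assumed), power would be 75.7% or 66.7%. If the current rule removed those same subjects from PP, it would be 79.4% or 76.5%. Power falls below 0.80 once about 0.6% are misclassified, so the limit to a recorded scabies indication should be kept.
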